1. PROTOCOL SUMMARY

1.1 Study Title

AI-Assisted Acute Myeloid Leukemia Evaluation With the Leukemia End-to-End Analysis Platform (LEAP) Versus Clinician-Only Assessment

1.2 Study Phase

Not Applicable (N/A)

1.3 Study Rationale

Acute promyelocytic leukemia (APL) is a rare but life-threatening subtype of acute myeloid leukemia (AML) that requires urgent diagnosis and treatment initiation. The diagnosis of APL relies on microscopic examination of bone marrow aspirate smears and molecular confirmation. However, inter-observer variability in microscopic evaluation has been reported, and molecular profiling requires additional time and resources. Artificial intelligence (AI) has the potential to augment diagnostic accuracy and efficiency in detecting APL from whole-slide images (WSIs). This study evaluates whether AI assistance through the Leukemia End-to-End Analysis Platform (LEAP) improves clinicians' diagnostic performance compared to unaided review.

1.4 Study Design

This is a prospective, randomized, crossover study, with AI assistance serve as the intervention. Clinicians review de-identified Wright-Giemsa-stained bone marrow WSIs under three conditions: (1) Unaided Review, (2) AI as Double-Check, and (3) AI as First Look. The order of unaided and AI-assisted reviews is randomized to minimize bias and learning effects.

1.5 Study Population

Participants (Readers): Board-certified pathologists and hematologists who routinely perform hematopathology diagnoses. Target enrollment: 10 participants (actual enrollment: 10 participants).

Cases (Pathology Slides): De-identified Wright-Giemsa-stained bone marrow aspirate WSIs with confirmed diagnoses. Each participant reviews 102 slides (34 slides per condition, stratified by APL status).

1.6 Study Duration

Study Start Date: September 9, 2025 (Actual)

Study Completion Date: October 10, 2025 (Actual)

1.7 Primary Objective

To evaluate the diagnostic performance of clinicians in detecting APL from bone marrow WSIs with and without AI assistance, measured by accuracy, sensitivity, specificity, positive predictive value (PPV), and negative predictive value (NPV).

1.8 Secondary Objectives

- To assess the time required to reach a diagnosis under different conditions
- To measure inter-observer variability across conditions
- To determine concordance between AI predictions and clinicians' diagnoses

- To evaluate decision-change rates after clinicians reviewed AI diagnostic results
- To quantify the net benefit of AI assistance on diagnostic accuracy
- To assess clinician confidence levels across conditions

1.9 Primary Endpoint

Diagnostic performance metrics (accuracy, sensitivity, specificity, PPV, NPV) for APL detection under unaided and AI-assisted conditions.

2. STUDY OBJECTIVES

2.1 Primary Objective

To evaluate and compare the diagnostic performance of clinicians in detecting acute promyelocytic leukemia (APL) from Wright-Giemsa-stained bone marrow whole-slide images under three conditions:

- **Condition X (Unaided Review):** Clinicians review slides without AI assistance.
- **Condition Y1 (AI as Double-Check):** Clinicians provide initial diagnosis, then review AI prediction and may revise their decision. Diagnoses made before and after AI exposure were recorded.
- **Condition Y2 (AI as First Look):** Clinicians review slides with AI prediction visible from the start.

2.2 Secondary Objectives

1. **Time efficiency:** To assess the average time required to reach a diagnostic decision under each condition.
2. **Inter-observer agreement:** To measure the consistency of diagnoses among clinicians across different conditions using inter-rater reliability metrics.
3. **AI-clinician concordance:** To determine the proportion of cases where AI predictions match clinicians' final diagnoses in each condition.
4. **Decision revision patterns:** To quantify how often clinicians change their initial diagnosis after viewing AI predictions in the "AI as Double-Check" condition.
5. **Net diagnostic benefit:** To calculate the overall improvement in diagnostic accuracy attributable to AI assistance.
6. **Confidence assessment:** To evaluate clinicians' self-reported diagnostic confidence across conditions and examine the relationship between confidence and accuracy.

3. STUDY DESIGN

3.1 Overall Design

This is a prospective, randomized, crossover study evaluating AI diagnostic assistance as the intervention. Each participating clinician (reader) reviews the same total number of cases (102

WSIs) but under three different conditions, with cases allocated such that no individual case is reviewed twice by the same reader.

3.2 Study Type

Study Type: Interventional

Study Design: Crossover assignment

Primary Purpose: To evaluate the effectiveness of AI diagnostic assistance

Study Phase: Not applicable (N/A)

Allocation: Randomized

Masking: Triple (Patients, Participating Clinicians, and Investigators)

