3.3 Study Arms and Randomization

Participants are randomized into one of two study arms, which differ in the order in which diagnostic conditions are presented:

Arm A: Unaided Review First, Then AI-Assisted Review (X → Y)

- **Block X (Unaided Review):** Participants review each slide in subset SX (34 slides) without AI assistance.
- **Block Y (AI-Assisted Review):** Participants review two subsets with AI assistance:
 - **Sub-block Y1 (AI as Double-Check):** Subset SY1 (34 slides) – Participants review each slide, provide an initial diagnosis, then view the AI-generated prediction and may revise their diagnosis if desired.
 - **Sub-block Y2 (AI as First Look):** Subset SY2 (34 slides) – Participants review each slide with the AI prediction visible from the beginning.

Arm B: AI-Assisted Review First, Then Unaided Review (Y → X)

- **Block Y (AI-Assisted Review):** Participants review two subsets with AI assistance, following the same procedure described for Block Y above.
 - **Sub-block Y1 (AI as Double-Check):** Subset SY1 (34 slides)
 - **Sub-block Y2 (AI as First Look):** Subset SY2 (34 slides)
- **Block X (Unaided Review):** Participants review each slide in subset SX (34 slides) without AI assistance, following the same procedure described for Block X above.

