3.7 Masking and Blinding

The study employs triple masking:

- **Patients:** Patients are blinded to the study arm to which their samples are assigned.
- **Care Provider:** Clinicians are blinded to the ground-truth diagnoses during all review sessions.
- **Investigator:** Study coordinators administering the session are blinded to the ground-truth diagnoses and to participants' arm assignments. In addition, statistical analysts are blinded to participant identities and arm assignments before results are finalized.

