5.2.3 Data Capture

The study platform automatically records for each slide:

- Reader ID (de-identified)
- Slide ID (de-identified)
- Study condition (X, Y1, or Y2)
- Diagnosis (APL vs. non-APL)
- Confidence score (1-5)
- Time from slide presentation to diagnosis submission (in seconds)
- For Condition Y1 only:
 - Pre-AI diagnosis and confidence score
 - Post-AI diagnosis and confidence score
- Timestamp of review

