7. STATISTICAL ANALYSIS PLAN

7.1 General Considerations

7.1.1 Analysis Populations

Intention to Treat (ITT): Participating clinicians will be analyzed according to their originally assigned study arm, regardless of any subsequent switch between arms.

Per-Protocol (PP): Participating clinicians will be analyzed according to the review protocol they actually followed. In cases of arm switching, standard causal inference methods will be applied to adjust for baseline covariates associated with switching behavior.

Primary Analysis Population: The ITT framework will be used for all primary and secondary analyses. Although arm switching is not anticipated, a supplementary PP analysis will be conducted if any switches occur.

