8.2 Data Monitoring

8.2.1 Monitoring Plan

This study does not employ an independent Data Monitoring Committee (DMC) as it is a minimal-risk AI user study. However, the principal investigator and study coordinators monitor:

- Participant enrollment and completion rates
- Data quality and completeness
- Technical issues with the study platform
- Any adverse events or participant concerns

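### The triple-masking label does not describe this design: readers know the condition on every slide, and the other masking is to block order or the reference diagnosis, not to condition

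*Combined protocol and SAP*

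**What the plan says.** The study type in section 3.2 carries the entry "Masking: Triple (Patients, Participating Clinicians, and Investigators". Section 3.1 names what is being tested: "This is a prospective, randomized, crossover study evaluating AI diagnostic assistance as the intervention". Section 3.3 defines the two arms as sequences, "which differ in the order in which diagnostic conditions are presented".

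Section 3.7 then explains the label party by party:

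- Readers: "Clinicians are blinded to the ground-truth diagnoses during all review sessions".
- Patients: masked to the arm of their own samples.
- Coordinators: masked to the reference diagnosis and to the reader's arm.
- Analysts: "statistical analysts are blinded to participant identities and arm assignments before results are finalized".

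Section 5.2.3 lists what the platform stores for each slide, including "Study condition (X, Y1, or Y2" and a review timestamp. Section 8.2.1 says that "the principal investigator and study coordinators monitor" enrolment, data quality and technical issues. Section 7.1.1 defines the intention-to-treat rule: "Participating clinicians will be analyzed according to their originally assigned study arm".

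**The concern.** A masking label tells the user of the results which parties were kept from knowing the treatment under comparison. Here that treatment is whether and when the AI prediction is displayed. The people who generate every diagnosis, review time and confidence score are the readers, and the label counts them as masked.

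Expectation effects are at stake. A reader who knows that no AI help is coming, or that it will follow the initial answer, may change pace, effort or stated certainty for that reason alone. Section 6.2.6 uses self-rated confidence to judge whether AI affects clinicians, and section 6.2.1 uses time to judge efficiency. Someone relying on the triple-masked label would take these results to be protected in a way that the design cannot provide.

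**Working it through.** The plan gives no figure for masking, so the check sets its sections side by side. A short enumeration then asks what the recorded fields would reveal.

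**Step 1. Extent.** Section 4.2.1 gives 34 + 34 + 34 = 102 slides per reader. With 10 readers, 10 × 102 = 1,020 reads, which reproduces the total in section 5.3. Each condition has 10 × 34 = 340 reads.

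**Step 2. Readers against condition.** Section 5.2.1 has the three conditions explained at orientation. Section 3.6 withholds the AI prediction in X, shows it after the initial diagnosis in Y1, and keeps it in view in Y2. A reader therefore knows the condition on 1,020 of 1,020 reads. Section 3.7 masks readers to the reference diagnosis, which is sound and necessary in a reader study but is a different thing.

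**Step 3. Patients.** Arms belong to readers (3.3), and the division of slides into the three subsets is drawn afresh for each reader (3.4). A given slide can be in X for one reader and in Y2 for another. It has no arm and no single condition from which a patient could be masked. Patients contribute slides from completed care (9.5.1).

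**Step 4. Coordinators and analysts.** Both are masked to arm, which is block order. Section 7.2.1 calculates the primary metrics by reader and condition, and section 7.3.4 needs the Y1 records before and after AI. The masking stated for these two roles therefore does not cover the variable that section 7 compares.

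**Step 5. Can order masking hold?** The possible sequences are A: X, Y1, Y2 and B: Y1, Y2, X. If the order within the AI block may vary, which the documents do not settle, add A: X, Y2, Y1 and B: Y2, Y1, X. The number of sequences from which the arm can be read with certainty is:

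| Fields available | Y1 always before Y2 | Y1/Y2 order varies |
|---|---|---|
| Condition and timestamp | 2 of 2 | 4 of 4 |
| Timestamp, X and Y2 coded, Y1 recognised by its pre/post fields | 2 of 2 | 2 of 4 |
| Condition without timestamp | 0 of 2 | 0 of 4 |

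Order masking can therefore hold if timestamps and block order are withheld, and it cannot hold if condition and timestamp are released together. Review time is stored as its own field in seconds (5.2.3), so withholding the timestamp does not remove the time outcome.

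**The case against.** The best defence is that section 3.7 says openly what each party is masked to, so a careful reader is not misled. Readers cannot be masked to a visible display, and no redesign would change that. Diagnoses and times are captured automatically, accuracy is scored against a laboratory reference standard, the tests are named in advance, and the 3-sigma rule for times is mechanical and reported both ways. Analyst discretion is small. All of this stands. It makes the fault one of labelling and reporting, and it lowers the value of masking the analyst. It does not make the label right, because the label in section 3.2 is a claim in its own right and section 3.7 does not support it for the intervention.

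Three stronger readings are tempting but not supported:

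- A reader might infer that coordinators and analysts were in fact unmasked to arm, because the platform stores condition and timestamp. The documents do not say who receives those fields together. Section 8.1.2 limits access to approved staff without giving rights by field, section 8.1.3 names no role for the review of captured data, and the monitoring in section 8.2.1 does not show access to both fields.
- A reader might infer that analyst masking to arm contradicts the intention-to-treat rule in section 7.1.1. Coded arm labels would satisfy both, none of the tests in section 7 has an arm term, and the per-protocol analysis arises only if readers switch arms. The plan is silent on coding, but that is a gap and not a contradiction.
- A reader might propose neutral condition labels together with each reader's sequence. That would defeat itself: X is always the first or last block and never the middle one, so with both arms present its label could be recognised.

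**Conclusion.** The label is wrong as written. Readers are open to condition on every read. The patient item describes an assignment that does not exist. The masking of coordinators and analysts concerns block order and, for coordinators, the reference diagnosis. Whether the order masking held in practice cannot be determined from the documents.

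The size of any resulting bias cannot be derived. Time and confidence are the most directly exposed. Diagnostic effort could also shift with knowledge of the condition, although scoring against a fixed reference leaves no room for judgement at that step. The conclusion rests on the condition and masking definitions in sections 3.3 to 3.7, not on any assumption about reader behaviour. It limits what may be claimed from the trial and does not fault the choice to run it open.

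**What to change.** 1. In sections 3.2 and 3.7, replace the word Triple with: open to condition for readers; readers and coordinators masked to the reference diagnosis; coordinators and analysts masked to block order. Delete the patient item.
2. To make the order masking hold, keep review timestamps and block order out of the files that coordinators and analysts use, and use coded arm labels for any by-arm analysis. State which fields each role receives. Section 10.2 records the study as complete, so if these fields have already been released together, the report should say so.
3. Report time and confidence as open-label outcomes, and give reader awareness of condition as a limitation.
4. Optional, if the analysis has not begun (the documents do not say): code the condition labels for the primary metrics and the time analysis, supplying neither sequence nor the Y1 pre/post fields until those results are locked. The gain is small because the tests and the outlier rule are already fixed.

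The cost is revised wording, a field restriction and, for the optional step, one recoding by data management. The downside is a less favourable masking label.

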3.3 Study Arms and Randomization

Participants are randomized into one of two study arms, which differ in the order in which diagnostic conditions are presented:

Arm A: Unaided Review First, Then AI-Assisted Review (X → Y)

- **Block X (Unaided Review):** Participants review each slide in subset SX (34 slides) without AI assistance.
- **Block Y (AI-Assisted Review):** Participants review two subsets with AI assistance:
 - **Sub-block Y1 (AI as Double-Check):** Subset SY1 (34 slides) – Participants review each slide, provide an initial diagnosis, then view the AI-generated prediction and may revise their diagnosis if desired.
 - **Sub-block Y2 (AI as First Look):** Subset SY2 (34 slides) – Participants review each slide with the AI prediction visible from the beginning.

Arm B: AI-Assisted Review First, Then Unaided Review (Y → X)

- **Block Y (AI-Assisted Review):** Participants review two subsets with AI assistance, following the same procedure described for Block Y above.
 - **Sub-block Y1 (AI as Double-Check):** Subset SY1 (34 slides)
 - **Sub-block Y2 (AI as First Look):** Subset SY2 (34 slides)
- **Block X (Unaided Review):** Participants review each slide in subset SX (34 slides) without AI assistance, following the same procedure described for Block X above.

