3.5 Study Workflow

Each participant completes a study session with the following structure:

1. **Randomization:** Participant is randomly assigned to Arm A or Arm B.
2. **Block sequence setting:** Participant completes blocks in the assigned order (X→Y or Y→X), depending on their Arm assignment.
3. **Slide sequence setting:** Participant review slides according to a predefined randomized order. The sequence is different for each participant.
4. **Pre-study briefing:** Participants receive instructions on the review platform; They also review two mock slides, one unaided, one aided, to familiarize themselves with the testing platform.
5. **Data recording:** For each slide, the system automatically records:
 - Diagnosis (APL vs. non-APL)
 - Confidence score (1-5 scale)
 - Time to decision (in seconds)
 - For Y1 (AI as Double-Check): both pre-AI and post-AI diagnoses and confidence scores

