3.6 AI System (LEAP) Implementation

The LEAP AI system generates diagnostic predictions independently for all 102 WSIs before the study session begins. During the study:

- **Condition X (Unaided):** AI predictions are not shown to the clinician
- **Condition Y1 (AI as Double-Check):** AI prediction is revealed only after the clinician submits their initial diagnosis
- **Condition Y2 (AI as First Look):** AI prediction is visible throughout the review

AI predictions are presented as binary classifications (APL vs. non-APL).

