5. STUDY PROCEDURES

5.1 Pre-Study Procedures

5.1.1 *AI Prediction Generation*

Prior to participant enrollment, the LEAP AI system generates diagnostic predictions for all 102 study cases. AI predictions are stored securely and revealed to participants only according to the assigned study condition.

5.1.2 *Randomization Procedures*

- Participants are randomized to Arm 1 (X→Y) or Arm 2 (Y→X) using a computer-generated randomization sequence with size 2 and size 4 blocks.
- For each participant, slides are randomly allocated to subsets SX, SY1, and SY2 with stratification by APL status
- All randomization is performed using validated software and documented in the study database.

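### No randomisation of the Y1/Y2 order is described; if Y1 always came first, the planned tests cannot separate a Y1–Y2 difference from learning or fatigue

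*Combined protocol and SAP*

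**What the plan says.** Every statement about order in the combined protocol and SAP concerns X against Y.

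- Section 1.4: "The order of unaided and AI-assisted reviews is randomized to minimize bias and learning effects".
- Section 3.3: "Participants are randomized into one of two study arms, which differ in the order in which diagnostic conditions are presented". Arm A is X→Y and Arm B is Y→X. Within Block Y the text says only "Participants review two subsets with AI assistance", then lists Y1 followed by Y2, in the same sequence in both arms.
- Section 3.5: "Participant completes blocks in the assigned order", again X→Y or Y→X. The next item adds "Participant review slides according to a predefined randomized order", different for each reader, without saying whether this runs within each sub-block or across the whole of Block Y.
- Section 5.1.2 allocates readers to the two sequences "using a computer-generated randomization sequence with size 2 and size 4 blocks". It gives no sequence for Y1 against Y2.

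On analysis, sections 7.2.1 and 7.3.1 plan a Friedman test with reader as the block. If it is significant, Wilcoxon signed-rank tests follow on every pair of conditions, so Y1 versus Y2 is a planned comparison. Section 7.3.3 compares concordance between pairs of conditions by permuting condition labels. None of these uses arm, period or position. All 102 slides are read in one session of about 2–3 hours (section 5.2.4), and section 9.5.1 names fatigue as a risk. Each review is timestamped (section 5.2.3).

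**The concern.** Section 1.4 treats learning over the session as a reason to randomise order, but that protection covers only unaided against AI-assisted review. In section 3.3 the list order carries the block order (X then Y in Arm A, Y then X in Arm B), so the natural reading is that Y1 was also done before Y2. On that reading no reader met Y2 before Y1, and any steady change over the session enters the Y2−Y1 estimates of performance, time and concordance in full. It could create a difference between the two ways of using AI, or hide one.

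The stake is the choice of workflow. Section 2.1 sets out to compare three conditions, and a reader of the results could take a Y1–Y2 difference, or its absence, as evidence about when to show the AI prediction.

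**Working it through.** The documents give no order-effect or power figure to reproduce. Inputs from them: 10 readers, 34 slides per condition, two sequences, two-sided alpha 0.05. Drift sizes and variances below are assumptions.

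**1. Block positions if Y1 is always first.** Arm A is X, Y1, Y2 (positions 1, 2, 3); Arm B is Y1, Y2, X (positions 1, 2, 3). The arm split is not stated. Blocks of 2 and 4 permit 6:4 or 4:6 if a last block of 4 is cut at reader 10.

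| Split A:B | X | Y1 | Y2 | Y2−Y1 | Y1−X | Y2−X | Pooled AI |
|---|---|---|---|---|---|---|---|
| 5:5 | 2.0 | 1.5 | 2.5 | +1.0 | −0.5 | +0.5 | 2.0 |
| 6:4 | 1.8 | 1.6 | 2.6 | +1.0 | −0.2 | +0.8 | 2.1 |
| 4:6 | 2.2 | 1.4 | 2.4 | +1.0 | −0.8 | +0.2 | 1.9 |

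At 5:5, for example, Y1 = (2+1)/2 = 1.5 and Y2 = (3+2)/2 = 2.5. A drift of d per block adds exactly d to Y2−Y1 at any split. At 5:5, Y1−X and Y2−X are shifted by −d/2 and +d/2, and pooled AI−X by zero. If Y2 was always first, the signs for Y1 and Y2 swap.

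**2. Illustration for time.** Assumptions: 5:5, Y1 first, slide log-SD 0.6, reader medians of 34 slides, no true Y1–Y2 difference, Friedman then exact Wilcoxon, 4,000 simulated trials. With a 10% speed-up per block, the share of trials with a false Y1–Y2 finding is:

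| AI effect on time | No reader variation | Reader variation (log-SD 0.10) |
|---|---|---|
| None | about 12% | about 5% |
| Both AI conditions 15% faster | about 26% | about 13% |

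A separate run used a log-SD of 0.15 per reader-condition median and no AI effect. The two-step rate was 2% with no drift and 4%, 9% and 21% at log drifts of −0.05, −0.10 and −0.20. The Wilcoxon test alone rejected in 5.1% with no drift. With Y1/Y2 order randomised per reader, that test stayed at 4.7–5.2% at every drift tried.

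**3. Drift can also hide a difference.** If Y2 is truly 20% faster than Y1 (ratio 0.80) and Y1 is as slow as unaided, speeding up 10% per block gives 0.80 × 0.90 = 0.72, and slowing down 10% gives 0.80 × 1.10 = 0.88. Under the same assumptions without reader variation, detection is 85% with no drift, 96% with speeding up and 30% with slowing down.

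**4. What adjustment can recover.** A model with 10 reader, 2 condition and 2 position parameters has full rank (14). Its Y2−Y1 estimate is the Arm A mean of (Y2 − 2Y1 + X)/3 plus the Arm B mean of (2Y2 − X − Y1)/3. Position terms cancel: (p3 − 2p2 + p1)/3 + (2p2 − p3 − p1)/3 = 0.

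- Variance in cell-variance units: unadjusted 2/10 = 0.200. Each arm's contrast has variance (1+4+1)/9 = 0.667 per reader. At 5:5 the total is 0.667/5 + 0.667/5 = 0.267, SE ratio √(0.267/0.200) = 1.155. At 6:4 it is 0.667/6 + 0.667/4 = 0.278, SE ratio 1.179.
- Carry-over c into Arm B's unaided block biases Y2−Y1 by −c/3, Y1−X by −c/3 and Y2−X by −2c/3.
- Carry-over from Y1 to Y2 has weight 1/3 + 2/3 = 1 in Y2−Y1, so none of it is removed.
- Two sequences by three positions give six means. An intercept, one sequence, two condition and two position terms fit all six exactly, so additivity cannot be checked.

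**The case against.** The strongest reply is that the premise is not established. A reader might infer from the bullets in section 3.3 that Y1 was done first for everyone. No sentence says so, and the randomised slide order in section 3.5 could have interleaved Y1 and Y2 slides. The term sub-block leans towards separate runs but does not settle it. This stands: what is certain is that the order is unstated, and the confounding is conditional on a fixed or unbalanced order.

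Second, the design protects the comparison that matters most. The summary objective and endpoint (sections 1.7 and 1.9) and net benefit (section 6.2.5) concern review with against without AI. For performance and time, Y1 versus Y2 is one of three follow-up pairs, tested only after a significant Friedman test. This also stands and limits the severity. It does not remove the point, because that pair is planned and the concordance test has no such prior step.

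Third, every drift size is assumed. Readers never learn the true diagnoses (section 3.7), practice slides and breaks may reduce drift, and learning and fatigue can oppose each other. The 15%-faster case also fits Y1 imperfectly, since "AI prediction is revealed only after the clinician submits their initial diagnosis". The rates are therefore illustrations, not estimates of what happened.

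Fourth, the adjusted model rests on assumptions that cannot be checked and can itself mislead. With no drift but carry-over of 0.2 log units into Arm B's unaided block, it gives about 15% false Y1–Y2 findings, when the planned two-step test gives 2–5% over the carry-over sizes tried. It can serve only as a supplement.

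**Conclusion.** The point holds in conditional form. The plan describes no randomisation or counterbalancing of Y1 against Y2. If Y1 was always first, the planned Y1-versus-Y2 tests of performance, time and concordance cannot distinguish the conditions from one block of learning or fatigue. Y1−X and Y2−X are each off by half a block, in opposite directions, at 5:5.

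Two wider readings are not supported. A reader might infer that AI-assisted versus unaided is confounded with order. Pooled over Y1 and Y2 it is balanced for linear drift at 5:5, and at 6:4 or 4:6 the gap is 0.3 of a block. A reader might also extend the problem to the Y1 before-and-after analyses (sections 7.3.4, 7.3.5.1 and 7.3.5.2). Those compare the same reader on the same slide and do not depend on the Y1/Y2 order.

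The severity is minor to moderate, limited mainly to one comparison. The documents give neither the size nor the direction of drift.

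**What to change.** 1. Establish each reader's Y1/Y2 order and the arm split from the platform records and timestamps, and report them. Because this reveals arm assignment, it should be done by someone other than the blinded analysts (section 3.7), or after the main results are final. If Y1 and Y2 slides were interleaved, or the order was balanced across readers, say so; nothing more is then needed for Y1 versus Y2.
2. If the order was fixed in either direction, or varied but was clearly unbalanced, label the Y1-versus-Y2 comparisons of performance, time and concordance exploratory. Report order as a limitation, including the imbalance in Y1−X and Y2−X.
3. In that case keep the planned tests and add, as a supplement only, a reader-level model with reader, condition and block position, coded from the order actually used. Apply the same blinding protection, and mark it as added after data collection, since sections 5.3 and 10.2 show all 10 readers complete. State that it assumes position effects common to both arms and no carry-over into Arm B's unaided block, that its additivity cannot be checked, and that it cannot remove carry-over from Y1 to Y2. A significant adjusted contrast therefore does not establish a Y1–Y2 difference.

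The cost is a sentence on order, a limitation sentence and one analysis on data already recorded. If Y1 was first, the adjusted standard error is about 15% larger at 5:5 and 18% at 6:4. No new data are needed.

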5.2.4 Session Duration

Participants complete all 102 slides in a single session. The expected duration is approximately 2-3 hours, with optional breaks permitted. The study platform allows participants to pause between slides but not during the review of an individual slide.

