9.5 Risk-Benefit Assessment

9.5.1 Risks

This study poses minimal risks to participants:

- Time commitment for the study session (2-3 hours)
- Potential fatigue from prolonged slide review
- Minimal risk of breach of confidentiality (mitigated by security measures)

Importantly, this study does not involve direct patient care, and no clinical decisions are based on study diagnoses. All patients have established ground-truth diagnoses and completed clinical management.

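### Unaided review never falls in the middle third of the session, so the randomised order cancels a straight-line session trend but not a curved one, and the analysis has no position term

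*Combined protocol and SAP*

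**What the plan says.** Section 1.4 gives the purpose of the randomised order: "The order of unaided and AI-assisted reviews is randomized to minimize bias and learning effects". Section 3.3 implements it with two sequences: "Participants are randomized into one of two study arms, which differ in the order in which diagnostic conditions are presented". Arm A reads the unaided block and then the AI block; Arm B does the reverse. On the unaided block: "Participants review each slide in subset SX (34 slides) without AI assistance". The AI block holds two further subsets of 34, Y1 (AI as double-check) and Y2 (AI as first look). Y1 is listed first in both arms, and nothing says that the order of Y1 and Y2 is randomised. Section 3.5 has readers complete the blocks in the assigned order.

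Section 5.2.4 adds: "Participants complete all 102 slides in a single session". It expects 2–3 hours and allows optional breaks. On preparation, section 3.5 says "They also review two mock slides, one unaided, one aided", and section 5.2.1 also offers practice on example slides from outside the study set. Section 9.5.1 lists as a risk: "Potential fatigue from prolonged slide review".

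Sections 7.2.1 and 7.3.1 compare X, Y1 and Y2 by a Friedman test on reader-by-condition values, then pairwise Wilcoxon tests. Neither section has a period, sequence or position term. Section 5.2.3 records a timestamp for every review.

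**The concern.** A two-order crossover balances order fully when the two treatments fill equal halves of the session. Here one fills a third and the other two thirds. Swapping the blocks moves X from one end of the session to the other and never into the middle. Unaided readings are therefore compared with AI readings that sit, on balance, nearer mid-session.

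If accuracy or speed changes along a curve over the 2–3 hours, part of that curve enters the unaided-versus-AI contrast, which is the purpose of the trial. It is a systematic error, so more readers or more slides would not shrink it, and the planned tests cannot reveal it. It needs no carry-over of knowledge from the AI block.

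**Working it through.** **Inputs from the documents.** Block sizes 34 (X), 34 (Y1) and 34 (Y2), and the orders X→Y and Y→X (3.3); one session (5.2.4); 10 readers (5.3). The plan's own counts reproduce: 3 × 34 = 102 slides, and 10 × 102 = 1,020 decisions.

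**Inputs assumed.** Five readers per arm; the size and shape of any drift; additive position effects; no true AI effect.

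**Step 1: layout.**

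| Slides | 1–34 | 35–68 | 69–102 |
|---|---|---|---|
| Arm A | X | AI | AI |
| Arm B | AI | AI | X |
| X readings (5:5) | 170 | 0 | 170 |
| AI readings (5:5) | 170 | 340 | 170 |

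Mean position is 51.5 for X and for pooled AI, so a linear trend cancels in that contrast.

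**Step 2: what remains.** Let f1, f2 and f3 be the mean position effects in the three thirds.

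- X = (f1 + f3)/2
- Pooled AI = [(f2 + f3)/2 + (f1 + f2)/2]/2 = (f1 + 2·f2 + f3)/4
- X − pooled AI = (f1 − 2·f2 + f3)/4

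This holds whatever the order of Y1 and Y2.

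**Step 3: the planned pairwise tests, if Y1 precedes Y2 as listed.**

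- Y1 − X = (f1 + f2)/2 − (f1 + f3)/2 = (f2 − f3)/2
- Y2 − X = (f2 + f3)/2 − (f1 + f3)/2 = (f2 − f1)/2

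Mean positions are then 34.5 for Y1 and 68.5 for Y2. Even a straight 10-point decline gives Y1 − X = +1.7 and Y2 − X = −1.7 points.

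**Step 4: accuracy, assumed curves.** Scale position as t = (p − 51.5)/50.5. The mean of t² is 0.491 in each outer third and 0.038 in the middle third. For a quadratic peak at mid-session, the share of the mid-to-end drop that goes to AI is (2 × 0.491 − 2 × 0.038)/4 = 0.227.

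| Assumed shape | Drop or trend (points) | Pooled AI − X (points) |
|---|---|---|
| Peak mid-session | 5 | +1.1 |
| Peak mid-session | 10 | +2.3 |
| Peak mid-session | 20 | +4.5 |
| Early warm-up that levels off | 10 | +0.8 (Y1 −0.4, Y2 +2.0) |
| Late fatigue | 10 | +1.1 (Y1 +2.4, Y2 −0.1) |
| Fatigue that levels off | 10 | −0.8 |
| Mid-session slump | 10 | −2.3 |

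The Y1 and Y2 figures assume Y1 first. For scale, one slide in 34 is 2.9 points.

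The Friedman test was simulated with no AI effect and a mid-session peak (3,000 runs, assumed peak accuracy 0.90, reader SD 0.03, Y1 first). It rejected in 4.8%, 5.0%, 9.2% and 13.3% of runs at drops of 0, 5, 10 and 20 points. At 10 and 20 points nearly all rejections had AI ahead.

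**Step 5: time, using the median per reader and condition as in 7.3.1.** The assumed curve is 80 + a·exp(−(p − 1)/15) seconds. The 80 s base lies within the range implied by 5.2.4: 7,200/102 = 71 s to 10,800/102 = 106 s per slide.

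| a (s) | Median by third (s) | X − average of Y1 and Y2 (s) | X − Y1 (s) | X − Y2 (s) |
|---|---|---|---|---|
| 20 | 86.66, 80.69, 80.07 | +1.3 | −0.3 | +3.0 |
| 60 | 99.98, 82.07, 80.21 | +4.0 | −0.9 | +9.0 |

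Check for a = 20: (86.66 − 2 × 80.69 + 80.07)/4 = 5.35/4 = 1.3.

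**Step 6: can it be adjusted?** A model with reader, condition and session third has full column rank: 13 of 13 columns with AI pooled, 14 of 14 with Y1 and Y2 separate (Y1 first). In units of residual SD, the standard error of X versus pooled AI rises from 0.387 to 0.447, a ratio of 1.155. For X versus Y1 or Y2 alone it rises from 0.447 to 0.516, the same ratio.

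**The case against.** A reader might infer that the schedule favours AI, since both a steep early learning curve and late fatigue make the ends of the session worse than the middle. The documents do not support that as a finding. They give no drift data, and the sign depends on the shape: a mid-session slump or fatigue that levels off reverses it. Nor does it hold for every planned test. With Y1 first, the early-learning curve makes X look slightly faster than Y1.

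There is mitigation. Practice slides are offered beyond the two mock slides, breaks and pauses between slides are allowed, and section 4.1.2 requires readers who know these smears. All of this makes a large drift less likely. Section 1.4 also says that order is randomised to minimise learning effects, not to eliminate them, and cancelling a linear trend is consistent with that. At an assumed 5-point drop the bias is under half a slide in 34 and the simulated error rate is essentially nominal. Finally, the study is complete, so the sequences cannot be changed.

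These points stand, and they limit the direction and size that can be claimed. They do not change the layout: no unaided reading exists in the middle third, and the analysis does not account for that.

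**Conclusion.** The concern holds as a structural limit on what the randomised order achieves. With 5:5 arms it removes a linear session trend from X versus pooled AI and leaves (f1 − 2·f2 + f3)/4 of any curved one. The direction cannot be known from the documents. Under assumed mid-session peaks of 5 to 20 points, the spurious gain for AI is about 1.1 to 4.5 points; under the opposite shape it is a loss of the same size. For the pairwise tests, both sign and size depend also on the Y1/Y2 order, which the plan should state.

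Even the cancellation of a linear trend rests on equal arms. Section 5.1.2 gives block sizes of 2 and 4 but no ratio. If a last block of 4 were cut short and the split were 6:4, a straight 10-point trend would leave about 1.0 point in X versus pooled AI.

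This does not show that any result is wrong. It is a possible bias in the main contrast that the planned analysis cannot detect and that existing data can address.

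**What to change.** - **Sections 7.2.1 and 7.3.1:** derive session third (slides 1–34, 35–68, 69–102) from the recorded timestamps. Report X versus Y1, X versus Y2 and X versus pooled AI, for accuracy, sensitivity, specificity and median time, from a within-reader model with session third as a factor. Place these beside the planned Friedman and Wilcoxon results and label them a sensitivity analysis, since the study is complete.
- **Section 3.3:** state the order of Y1 and Y2 that was used, and report the number of readers per arm.
- **Section 1.4:** limit the claim about learning effects to linear order effects.
- **Any repeat study:** include orders that place X in the middle third. Equal use of all six orders of X, Y1 and Y2 gave zero order bias for every curve tried. Ten readers is not a multiple of six, so balance would be approximate.

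The cost is some SAP wording and one extra model on data already captured. The adjusted standard error is about 15% larger at 5:5 for the same residual SD. The model assumes that position effects add to condition effects and that there is no carry-over. With no unaided readings in the middle third, additivity cannot be checked there.
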